4.2 Ineligibility Criteria

Patients who fulfill any of the following criteria are not eligible for admission to the study:

- 4.2.1 Patients with a history of other malignancies, except: adequately treated non-melanoma skin cancer, curatively treated in-situ cancer of the cervix, or other solid tumours curatively treated with no evidence of disease for ≥ 5 years.
- 4.2.2 Any previous treatment with a PD1 or PD-L1 inhibitor, including durvalumab, or an anti-CTLA4, including tremelimumab.
- 4.2.3 History of primary immunodeficiency, history of organ transplant that requires therapeutic immunosuppression or prior history of severe (grade 3 or 4) immune mediated toxicity from other immune therapy.
- 4.2.4 Current or prior use of immunosuppressive medication within 28 days before the first dose of durvalumab or tremelimumab, with the exceptions of intranasal and inhaled corticosteroids or systemic corticosteroids at physiological doses, which are not to exceed 10 mg/day of prednisone, or an equivalent corticosteroid.
- 4.2.5 Active or prior documented autoimmune or inflammatory disorders (including inflammatory bowel disease (e.g. Crohn's disease, ulcerative colitis) within the past 2 years NOTE: Subjects with vitiligo, Grave's disease, or psoriasis not requiring systemic treatment (within the past 2 years) are not excluded.

- 4.2.6 Patients with active or uncontrolled intercurrent illness including, but not limited to:
- cardiac dysfunction (symptomatic congestive heart failure, uncontrolled hypertension, unstable angina pectoris, cardiac arrhythmia)
 - active peptic ulcer disease or gastritis,
 - active bleeding diatheses
 - psychiatric illness/social situations that would limit compliance with study requirements or compromise the ability of the subject to give written informed consent
 - known history of previous clinical diagnosis of tuberculosis
 - known human immunodeficiency virus infection (positive HIV 1/2 antibodies)
 - known active hepatitis B infection (positive HBV surface antigen (HBsAg). Patients with a past or resolved HBV infection (defined as presence of hepatitis B core antibody (anti-HBc) and absence of HBsAg) are eligible.
 - known active hepatitis C infection. Patients positive for hepatitis C (HCV) antibody are eligible only if polymerase chain reaction is negative for HCV RNA.
- 4.2.7 History of leptomeningeal carcinomatosis.
- 4.2.8 Symptomatic or uncontrolled brain metastases requiring concurrent treatment, inclusive of but not limited to surgery, radiation and/or corticosteroids.
- 4.2.9 Receipt of live attenuated vaccination (examples include, but are not limited to, vaccines for measles, mumps, and rubella, live attenuated influenza vaccine (nasal), chicken pox vaccine, oral polio vaccine, rotavirus vaccine, yellow fever vaccine, BCG vaccine, typhoid vaccine and typhus vaccine) within 30 days prior to randomization.
- 4.2.10 Pregnant or lactating women.
- 4.2.11 Any active disease condition which would render the protocol treatment dangerous or impair the ability of the patient to receive protocol therapy.
- 4.2.12 Any condition (e.g. psychological, geographical, etc.) that does not permit compliance with the protocol.
- 4.2.13 Receipt of anti-cancer chemotherapy or biologic therapy within the lesser of i) 21 days, or ii) the usual cycle length of the regimen (e.g. 14 days for FOLFOX), prior to the first planned dose of durvalumab or tremelimumab. An exception is made for capecitabine and regorafenib, where a minimum of 10 days since last dose must be observed prior to the first planned dose of durvalumab or tremelimumab.
- 4.2.14 Receipt of radiotherapy or investigational agents within four weeks of first planned dose of durvalumab or tremelimumab, with the exception of a single dose of radiation up to 8 Gray (equal to 800 RAD) with palliative intent for pain control up to 14 days before randomization.
- 4.2.15 Any unresolved toxicity (CTCAE grade 2) from previous anti-cancer therapy. However, patients with irreversible toxicity that is not reasonably expected to be exacerbated by the investigational products in the Investigator's opinion may be included (e.g. hearing loss, peripheral neuropathy).

5.0 PATIENT EVALUATION FLOWSHEET: PRE-TREATMENT, ON STUDY, AND AFTER TREATMENT

All patients entered on study must be evaluated according to the schedule outlined below with documentation submitted according to the schedule in Appendix IV.

5.1 Patient Evaluation Flowsheet: Pre-study (Baseline) and Post-randomization Follow-up
For Patients Randomized to Best Supportive Care (Arm 1)

| Required Investigations | PRE-STUDY (≤ 14 days prior to randomization, unless otherwise indicated) | PRIOR to objective disease progression (timing from randomization) | | AFTER objective disease progression (timing from randomization) |
|---|---|---|--|--|
| | | Every 4 weeks until objective disease progression | Every 8 weeks until objective disease progression (maintain schedule even if clinic visits are delayed) ³ | Every 12 weeks |
| History and Physical Exam | | | | |
| Including: height (baseline only), weight, ECOG performance status, clinical tumour measurements (if applicable) | X | X | | |
| Vital Signs (blood pressure, heart rate, temperature) | X | X | | |
| Concomitant Medications | X | X | | |
| Overall Survival | | | | |
| Survival Status Assessment | | X | X | X ¹ |
| Hematology | | | | |
| CBC, differential (including lymphocytes), platelets | X | X | | |
| Coagulation | | | | |
| PTT, PT/INR | X | X | | |
| Biochemistry | | | | |
| Serum Creatinine, Chloride, Sodium, Potassium, Calcium, Magnesium, Bilirubin, ALP, AST and ALT, LDH, Albumin, TSH ² , Amylase, Lipase, Serum CEA | X | X | | |
| Creatinine Clearance (calculated) | X | as clinically indicated | | |
| Glucose | X | as clinically indicated | | |
| Radiology³ | | | | |
| Chest/abdomen/pelvis CT or MRI scan ³ | X ≤ 28 days | | X ³ | |
| Other scans as necessary to document all measurable and non-measurable disease ³ | X ≤ 28 days | | | |
| Other Investigations | | | | |
| Pregnancy Test ⁴ | X | | | |
| ECG | X | as clinically indicated | | |
| Dipstick Urinalysis (including protein, specific gravity, glucose and blood) | X | | | |

table continued on next page ...

| Correlative Studies | | | |
|--|--|---|--|
| Archival Tissue Sample ⁵ (mandatory) | Availability of sufficient tissue must be confirmed prior to randomization | Submit tissue within 4 weeks of randomization | |
| Whole blood, plasma and serum ^{5,6} (mandatory) | X | To be done at 8 weeks, and at the time of objective disease progression ⁷ , if not already done | |
| Adverse Events | | | |
| Adverse Event Assessment ⁸ | X (To document residual adverse events from previous therapy and baseline symptoms) | X To be evaluated continuously for adverse events (until objective disease progression) | |
| Quality of Life | | | |
| EORTC QLQ C30 ⁹ | X | At 4, 8, 12, 16 and 24 weeks after randomization, then every 12 weeks thereafter (until deterioration to ECOG PS 4 or hospitalization for end of life care) | |
| 
 1. In the event that patient is unable to attend clinic, post-progression follow-up may be by means of telephone contact. 2. If abnormal, T3 and T4 must be measured. 3. To ensure comparability, scans must identify and report each lesion at baseline and at reassessment. These scans must be performed using identical technique (i.e. scans performed immediately following bolus contrast administration using a standard volume of contrast, the identical contrast agent, and preferably the same scanner). Tumour evaluations must be consistently performed every 8 weeks (i.e. at 8 weeks, 16 weeks, 24 weeks, 32 weeks etc. from randomization) until objective disease progression is documented (as described in Section 8). Sites should adhere to this calendar-based schedule regardless of any delays in clinic visits. If a radiology scan is done off schedule, future protocol-required scans should still be performed based on the original schedule, i.e. every 8 weeks counting from randomization (not from the date of the off schedule scan). 4. For women of childbearing potential only. May be urine or serum. Pregnancy test (in women of childbearing potential), as part of Pre-Study Evaluation, may include an ultrasound to rule-out pregnancy. 5. See Section 12.0 and the CO.26 Correlative Studies Laboratory Manual for details. 6. Details for collection, processing, storing, and shipping these samples will be provided in the CO.26 Correlative Studies Manual 7. Whole blood, plasma and serum should be obtained as close to the time of objective progression as possible and should be done within 28 days (e.g. at the next clinic visit). Blood for correlatives done within 28 days PRIOR to date of progression does not need to be repeated. 8. Adverse Events to be evaluated using the NCI Common Terminology Criteria for Adverse Events (CTCAE v4.0) (see Appendix V). 9. To be completed by patient in clinic. | | | |

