| 
 All patients will be seen at 4 weeks after the end of the last cycle date. Thereafter, continued follow-up is not required for patients who go off protocol treatment with unequivocal progressive disease, except to document ongoing toxicities (until resolved to < grade 2) and late toxicities (including second malignancies). For patients who go off protocol treatment with CR, PR, or SD ongoing, follow-up will be required every 12 weeks until relapse (see Appendix I for investigations to be performed). Death Report will be required for all patients. Due within 2 weeks of knowledge of death (see Appendix IV - Documentation for Study). Timing of Day 1 Assessments: Pre-treatment blood draws and physical exams may be done one working day prior to treatment if necessary, and when treatment is to begin on a Monday, may be done on the previous Friday (maximum 72 hours prior to treatment). In order to ensure that nadir counts are not missed, every effort should be made to do interim blood draws within 24 hours of the day specified in the protocol. If a patient shows an AST or ALT ≥ 3 x ULN together with total bilirubin ≥ 2 x ULN, refer to Appendix III for further instructions on cases of increases in liver biochemistry and evaluation of Hy's Law. These cases should be reported as SAEs if, after evaluation, they meet the criteria for a Hy's law case or if any of the individual liver test parameters fulfill any of the SAE criteria. Note: Labs do not need to be repeated Day 1, Cycle 1. In order to ensure that nadir counts are not missed, every effort should be made to do interim blood draws within 24 hours prior to the day specified in the protocol. Vital signs are to be monitored before, during, and after the infusion of tremelimumab and durvalumab with assessment of vital signs to be collected ≤ 30 minutes prior to start of infusion then every 30 ± 5 minutes during infusion and observation periods. A 1-hour observation period is recommended after the first infusion of tremelimumab, during which time durvalumab may be administered (see Section 7.1.3). A second 1-hour observation period is recommended after the first infusion of durvalumab. If no clinically significant infusion reactions are observed during or after the first cycle of tremelimumab and durvalumab, subsequent infusion observation periods can be at the Investigator's discretion but are recommended to be of 30 minutes, i.e., 30 minutes after tremelimumab infusion, during durvalumab infusion, and for 30 minutes after durvalumab infusion. For patients who receive only durvalumab, the recommended observation period is 30 minutes after infusion. In the event that patient is unable to attend clinic, post-progression follow-up may be by means of telephone contact. Hematology, Coagulation and Biochemistry investigation to be done after objective progression ONLY if there are ongoing hematologic AEs that are related to protocol treatment. If abnormal, T3 and T4 must be measured. To ensure comparability, scans must identify and report each lesion at baseline and at reassessment during treatment. These scans must be performed using identical technique (i.e. scans performed immediately following bolus contrast administration using a standard volume of contrast, the identical contrast agent, and preferably the same scanner). Tumour evaluations must be consistently performed every 8 weeks (i.e. at 8 weeks, 16 weeks, 24 weeks, 32 weeks etc. from randomization) until objective disease progression is documented (as described in Section 8). Sites should adhere to this calendar-based schedule regardless of any delays in treatment. If a radiology scan is done off schedule, future protocol-required scans should still be performed based on the original schedule, i.e. every 8 weeks counting from randomization (not from the date of the off schedule scan). For women of childbearing potential only. May be urine or serum. Pregnancy test (in women of childbearing potential), as part of Pre-Study Evaluation, may include an ultrasound to rule-out pregnancy. See Section 12.0 and the CO.26 Correlative Studies Laboratory Manual for details. Whole blood, plasma and serum should be obtained as close to the time of objective progression as possible and should be done within 28 days (e.g. at the next clinic visit). Blood for correlatives done within 28 days PRIOR to date of progression does not need to be repeated. Adverse Events to be evaluated using the NCI Common Terminology Criteria for Adverse Events (CTCAE v4.0) (see Appendix V). See Section 7 and Appendix III for additional monitoring of patients with toxicity. Follow every adverse event felt related to study therapy until resolved to ≤ grade 2 – i.e. follow-up every 12 weeks until deterioration to ECOG PS 4 and/or end of life care or until all toxicities thought to be possibly-, probably-, or definitely-related to durvalumab or tremelimumab have resolved, returned to baseline, or been deemed irreversible, whichever is longer. To be completed by patient in clinic. | | | | | | |

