8.2 Response and Evaluation Endpoints

Response and progression will be evaluated in this study using the revised international criteria (1.1) proposed by the RECIST (Response Evaluation Criteria in Solid Tumours) committee as well as the Immune-Related Response Criteria (irRECIST). In the event of disease progression using the RECIST 1.1 criteria (unconfirmed PD (uPD)), investigators should continue treatment, if the patient is clinically stable (i.e. stable performance status and disease related symptoms) until disease progression is confirmed at a subsequent scan at least 4 weeks later (unequivocal confirmed disease progression (cPD)). This is particularly important for patients in whom pseudoprogression may have occurred. Follow up response assessments must be continued until unequivocal disease progression has occurred.

8.2.1 Measurable Disease.

Measurable *tumour lesions* are defined as those that can be accurately measured in at least one dimension (longest diameter to be recorded) as ≥ 20 mm with chest x-ray and as ≥ 10 mm with CT scan or clinical examination. Bone lesions are considered measurable only if assessed by CT scan and have an identifiable soft tissue component that meets these requirements (soft tissue component ≥ 10 mm by CT scan). *Malignant lymph nodes* must be ≥ 15 mm in the short axis to be considered measurable; only the short axis will be measured and followed. All tumour measurements must be recorded in millimetres (or decimal fractions of centimetres). Previously irradiated lesions are not considered measurable unless progression has been documented in the lesion.

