7.9.2 Data Sets

The analyses of quality of life data will be restricted to randomized patients who have a measurement at baseline and at least one measurement after baseline.

The QOL assessment is performed prior to randomization and during chemotherapy/BSC at 4, 8, 16, and 24 weeks from randomization. Since exact time of assessment may vary from subject to subject, it is necessary to provide a window for each QOL time point. What follows is a description of how to assign a questionnaire to a discrete time point:

Time Point	Windows (i.e., time periods)
Baseline	14 days prior to up to the day of randomization
Week 4	2 weeks - < 6 weeks
Week 8	6 weeks - < 10 weeks
Week 12	10 weeks - < 14 weeks
Week 16	14 weeks - < 20 weeks
Week 24	20 weeks - < 28 weeks

If more than one questionnaire is available for the baseline window, then the latest non-missing measurement, per question, will be considered. If more than one questionnaire is available at a time point other than baseline, then the average (per question) of the non-missing measurements will be used.

Summary statistics, plots and longitudinal comparisons will be based on changes of the quality of life scores from baseline.

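### Progressed BSC patients have no scheduled visit in the week-16 QoL window, so in-clinic completion risks a higher missing rate on BSC at a primary QoL time point

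*Protocol*

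**What the plan says.** **QoL schedule.** The QoL row of Protocol 5.1 (Arm 1) places the QLQ-C30 "At 4, 8, 12, 16 and 24 weeks after randomization, then every 12 weeks thereafter" and continues it "until deterioration to ECOG PS 4 or hospitalization for end of life care". Progression does not end it. Footnote 9 sets the mode: "9. To be completed by patient in clinic". Protocol 5.2 (Arm 2) has the same row, and its footnote 14 says "To be completed by patient in clinic".

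**Visit schedule, BSC.** Visits are 4-weekly until objective progression. The column headed "AFTER objective disease progression (timing from randomization" then gives contact every 12 weeks, and footnote 1 adds: "In the event that patient is unable to attend clinic, post-progression follow-up may be by means of telephone contact".

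**Visit schedule, Arm 2.** After a first RECIST 1.1 progression, Protocol 8.2 says "investigators should continue treatment, if the patient is clinically stable", and 10.2 says much the same. Patients on drug attend on Day 1 of each 4-week cycle. After stopping drug, 5.2 places a visit 4 weeks after the end of the last cycle, whereas Appendix IV places it 4 weeks after the last infusion. Contact is 12-weekly after that.

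**Analysis.** SAP 7.9.4 makes deterioration in physical function and global health status at weeks 8 and 16 the primary QoL endpoints, compared by Fisher's exact test. SAP 7.9.2 sets the week-16 window at "14 weeks - < 20 weeks".

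**The concern.** The QoL schedule and the visit schedule do not fit together after progression, and the misfit differs by arm. A BSC patient who progressed at the week-8 scan owes a form at week 16, to be completed in clinic, but no attendance is planned between weeks 12 and 24. An Arm 2 patient who progressed at the same scan and stays on drug is in clinic on Day 1 of cycle 5, which is week 16.

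SAP 7.9.4 compares the forms that arrive. SAP 7.9.1 handles missing items within a questionnaire, but nothing is said about missing questionnaires. Patients who have progressed are probably the likelier to have deteriorated. If their forms are lost at a higher rate on BSC, the observed BSC deterioration proportion is too low and BSC looks better than it is. Time to definitive deterioration, censored at the last QoL assessment, is exposed in the same way. This loss would come from the visit calendar, among patients alive and able to answer.

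**Working it through.** **1. BSC contacts after progression.** Every 12 weeks from randomization gives weeks 12, 24, 36. None satisfies 14 ≤ t < 20. Appendix IV describes the Short Follow-up Report as 12-weekly after progression without naming the anchor. Counted from progression at the week-8 scan, that gives 8 + 12 = 20, still outside. Only progression documented from week 2 to before week 8 would give an in-window contact.

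**2. Arm 2, on drug past progression.** Day 1 of cycle 5 falls at week 4 × 4 = 16, in the window.

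**3. Arm 2, progressed and off drug after k cycles.** By the flowsheet the first visit is at week 4k + 4. By Appendix IV it is at 4(k − 1) + 4 = 4k. Contacts then follow every 12 weeks.

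| Cycles | Flowsheet anchor (weeks) | In window? | Appendix IV anchor (weeks) | In window? |
|---|---|---|---|---|
| 1 | 8, 20 | no | 4, 16 | yes |
| 2 | 12, 24 | no | 8, 20 | no |
| 3 | 16, 28 | yes | 12, 24 | no |
| 4 | 20, 32 | no | 16, 28 | yes |

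The week-16 contact after one cycle is a 12-weekly one, which 5.2 allows by telephone.

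**4. Patients alive at week 16.** The plan gives no QoL sample size or power, so I borrow the OS design of Protocol 13.3. It is internally consistent: 4.5/0.65 = 6.9 months, and Schoenfeld's formula with 2:1 allocation gives (1.645 + 0.842)² / [(2/3)(1/3)(ln 0.65)²] = 150 deaths, as stated. Week 16 is 16 × 7/30.4375 = 3.68 months. With exponential survival:

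- BSC: exp(−ln 2 × 3.68/4.5) = 0.567, × 60 = 34 patients
- Arm 2: exp(−ln 2 × 3.68/6.9) = 0.691, × 120 = 83 patients

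**5. Missing forms, under assumptions.** The documents give none of these three quantities:

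- p: share of survivors progressed before the window (30–70%, same in both arms)
- r: share of patients without a visit who still return a form (0–50%, same in both arms)
- c: share of progressed Arm 2 patients with an in-window visit (0–75%)

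The missing rate is p(1 − r) on BSC and p(1 − c)(1 − r) on Arm 2.

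| p | r | c | BSC missing | Arm 2 missing |
|---|---|---|---|---|
| 30% | 50% | 75% | 15% (5) | 4% (3) |
| 50% | 0 | 0 | 50% (17) | 50% (41) |
| 50% | 0 | 50% | 50% (17) | 25% (21) |
| 50% | 0 | 75% | 50% (17) | 12% (10) |
| 70% | 0 | 0 | 70% (24) | 70% (58) |

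Over the whole grid BSC loses 15–70% (5–24 patients) and Arm 2 loses 4–70% (3–58 patients). The BSC rate is the higher one whenever c > 0. The BSC count is the higher one only if 34 > 83(1 − c), that is c > 1 − 34/83 = 59%.

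**The case against.** **The assessment is required.** The QoL row itself schedules week 16 after progression, and Section 5.0 says patients must be evaluated to that schedule. Besides that row, the 12-weekly BSC column marks only survival status, so it need not limit QoL attendance. This stands as far as it goes: the assessment is not absent. But a site is told to obtain a form in clinic in a week for which no clinic visit is planned.

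**Appendix VI softens the in-clinic rule.** It allows mail or telephone when a form was missed at a clinic attendance, supplied forms for a long absence, and take-home when a patient declines in clinic. It also provides for patients physically unable to complete the form, and the CO.26 cover page has boxes for home, clinic and another centre. Loss is therefore not automatic. None of these routes expressly covers a patient with no scheduled visit, however. Take-home for want of a return visit is described only for some trials, and the CO.26 flowsheets do not invoke it.

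**Two stronger readings a reader might infer.** One is that progressed patients have no week-16 visit unless they stay on drug. For Arm 2 the table in step 3 shows otherwise: by the flowsheet those who stop after 3 cycles are due in the window, and by Appendix IV those who stop after 1 or 4 have a contact there. The other is that most of the missing forms will be on BSC. With twice as many patients on Arm 2, that holds only if c exceeds about 59%, and the documents give no value for c.

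**Importance.** QoL is a tertiary objective, and in SAP 7.9.4 the word primary ranks endpoints within QoL only. Week 8 is largely unaffected, and a patient who first progresses at the week-16 scan is still on the pre-progression schedule. SAP 7.9.3 reports compliance by time point, and Table 62 gives it by arm. All of this stands. The table would show a difference in missingness but would not correct for it.

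**Conclusion.** The point holds as a conflict between two schedules that bears unequally on the arms. By the flowsheet, progressed BSC patients have no scheduled visit in the week-16 window. Arm 2 patients on drug, and some who have stopped, do. In-clinic completion therefore risks a higher missing rate on BSC at one of the two primary QoL time points.

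The size is not derivable from the documents. The 50% against 25% figure is an illustration at p = 50%, r = 0, c = 50%. That the BSC rate is higher rests on c > 0 and on p and r being equal across arms. The direction of bias, towards BSC looking better, rests on progressed patients being likelier to have deteriorated, which is plausible but not shown. The OS comparison is unaffected. This is a cheap improvement to a tertiary objective.

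**What to change.** **Protocol.** Change footnote 9 in 5.1 and footnote 14 in 5.2 to say that, when no clinic visit falls within the QoL window, the form is completed by mail or telephone as in Appendix VI section 5A, regardless of progression. State the windows there, since at present they stand only in SAP 7.9.2. Reconcile the two Arm 2 follow-up anchors, end of last cycle in 5.2 and last infusion in Appendix IV.

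**SAP.** A footnote cannot recover forms already missed. SAP 2.1 gives closure to randomization as June 29, 2017, so the last week-16 window ended 20 weeks later, in mid-November 2017. Where collection is over, report week-16 missingness by arm and by progression status among patients alive, alongside Table 62. Add a sensitivity analysis for missing forms to 7.9.4, for example counting a missing form in a progressed, living patient as deterioration in both arms.

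**Cost.** The protocol change costs two footnotes and one mailed or telephoned form per affected patient. Its downside is mixed modes of completion; the cover page already records the place, and Appendix VI already asks sites to note telephone completion. The SAP change costs one tabulation and one further analysis of data already held.
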